6.2.4 Management of Dermatologic Toxicity

Treatment-emergent rash (eg, maculopapular or purpura) has been associated with MPDL3280A. The majority of cases of rash were mild in severity and self-limited, with or without pruritus.

A dermatologist should evaluate persistent and/or severe rash or pruritus. A biopsy should be considered unless contraindicated. Dermatologic toxicity and rash should be managed according to Table 14.

Description	Management
Grade 1 mild < 10% BSA	 Continue MPDL3280A. Symptomatic therapy with antihistamine PRN; Consider topical steroids and/or other symptomatic therapy (eg, antihistamines).
Grade 2 moderate 10%-30% BSA	 Continue MPDL3280A; Consider dermatologist referral; Administer topical steroids; Consider higher potency topical steroids if rash unresolved.
Grade 3 severe > 30% BSA	 Hold MPDL3280A; Consult dermatologist; Administer oral prednisone 10 mg or equivalent. If rash unresolved after 48-72 hours, administer oral prednisone 60 mg or equivalent; Restart MPDL3280A if rash resolved and systemic dose is ≤ 10 mg oral prednisone equivalent per day; Permanently discontinue MPDL3280A for life-threatening immune-related dermatologic toxicity.

Table 14:Management Guidelines for Rash

BSA, body surface area; PRN, as needed.

6.2.5 Management of Endocrine Toxicity (Hypothyroidism)

Hypothyroidism has been associated with the administration of MPDL3280A.

Patients with unexplained symptoms such as fatigue, myalgias, impotence, mental status changes, or constipation should be investigated for the presence of thyroid, pituitary, or adrenal endocrinopathies, as well as for hyponatremia or hyperkalemia. An endocrinologist should be consulted if an endocrinopathy is suspected. Thyroid-stimulating hormone (TSH) and free T4 levels should be obtained to determine whether thyroid abnormalities are present. TSH, prolactin, and a morning cortisol level will help to differentiate primary adrenal insufficiency from primary pituitary insufficiency.

Hypothyroidism should be managed according to Table 15.

 Table 15:
 Management Guidelines for Hypothyroidism

Description	Management
TSH elevated, asymptomatic	Continue MPDL3280A;
	• Start thyroid replacement hormone (as per institutional guidelines);
	Monitor TSH weekly.
TSH elevated, symptomatic	Hold MPDL3280A;
	• Consider referral to an endocrinologist;
	• Start thyroid replacement hormone (as per institutional guidelines);
	• Monitor TSH weekly;
	• Restart MPDL3280A when symptoms are controlled by thyroid replacement and TSH levels are decreasing.

TSH, thyroid-stimulating hormone.

6.2.6 Management of Pericardial and Pleural Effusions

Pericardial involvement with associated effusions is common in patients with NSCLC and have the theoretical potential to be exacerbated by inflammation associated with antitumor immunity following PD-L1 blockade. Patients presenting with dyspnea, chest pain, or unexplained tachycardia should be evaluated for the presence of a pericardial effusion. Patients with preexisting pericardial effusion should be followed closely for pericardial fluid volume measurements and impact on cardiac function. When intervention is required for pericardial effusions, appropriate workup includes cytology, lactate dehydrogenase (LDH), glucose, cholesterol, and cell count. For patients with a pericardial effusion causing end-diastolic right ventricular collapse, treatment may be restarted following the placement of a pericardial window, demonstration of hemodynamic stability, and resolution of right ventricular dysfunction.

6.2.7 Management of Potential Pancreatic Toxicity

Symptoms of abdominal pain associated with elevations of amylase and lipase, suggestive of pancreatitis, have been associated with the administration of other immunomodulatory agents.
The differential diagnosis of acute abdominal pain should include pancreatitis. Appropriate workup should include an evaluation for obstruction, as well as serum amylase and lipase tests.

Pancreatic toxicity should be managed according to Table 16.

 Table 16:
 Management Guidelines for Amylase/Lipase Abnormalities

Description	Management
Amylase/lipase (> ULN and $\leq 2 \times$ ULN) and asymptomatic	Continue MPDL3280A;Monitor amylase/lipase levels prior to dosing.
Amylase/lipase (> $2 \times ULN$ to $\leq 5 \times ULN$) and asymptomatic	 Continue MPDL3280A; Monitor amylase/lipase weekly; Consider oral prednisone 10 mg daily or equivalent for prolonged elevation (eg, more than 3 weeks).
Amylase/lipase (> 5 × ULN) and asymptomatic	 Hold MPDL3280A; Monitor amylase/lipase every other day and consider oral prednisone 60 mg daily or equivalent; Consult a gastroenterologist; Resume MPDL3280A dosing when lipase/amylase levels are less than 2 × ULN.
Autoimmune pancreatitis (abdominal pain and raised amylase/lipase levels)	 Hold MPDL3280A; Consult a gastroenterologist; Consider administering IV steroids (prednisone equivalent of 60 mg/day) followed by taper over 2-4 weeks; Resume MPDL3280A when enzyme levels are less than 2 × ULN and patient is asymptomatic; Permanently discontinue MPDL3280A for life threatening immune related pancreatitis.

IV, intravenous; ULN, upper limit of normal.

6.2.8 Management of Potential Ocular Toxicity

An ophthalmologist should evaluate visual complaints. Uveitis or episcleritis may be treated with topical corticosteroid eye drops. MPDL3280A should be permanently discontinued for immune-mediated ocular disease that is unresponsive to local immunosuppressive therapy.

Ocular toxicity should be managed according to Table 17.

Table 17: Management Guidelines for Ocular Toxicities

Description	Management
Symptomatic: autoimmune uveitis, iritis, or episcleritis	 Hold MPDL3280A; Consult ophthalmologist and start topical corticosteroid eye drops; MPDL3280A may be restarted following resolution of the events and discussions with the Medical Monitor; Permanently discontinue MPDL3280A for immune-mediated ocular disease that is unresponsive to local immunosuppressive therapy.

6.3 Overlapping Expected or Potential Toxicities

Guidelines for the management of specific expected or potential overlapping toxicities for rociletinib and MPDL3280A are described in Table 18.

Table 18:Management of Overlapping Toxicities

Toxicity	Attribution to both agents
Rash/Skin Toxicity:	Grade 2: continue both agents; initiate supportive care.
	Grade 3:
	 Obtain dermatology consult;
	■ Hold rociletinib and MPDL3280A until resolved to ≤ Grade 1, then reinitiate rociletinib at a dose agreed upon with the Sponsor's Medical Monitor; (dose delays longer than 14 days also require discussion with the Medical Monitor);
	 Restart MPDL3280A if rash does not occur within 14 days of rociletinib re-initiation;
	 Hold rociletinib and permanently discontinue MPDL3280A if the patient experiences recurrent Grade ≥ 3 skin toxicity. When rash is Grade 1, restart rociletinib at previous dose. If Grade ≥ 3 rash recurs, rociletinib should be discontinued permanently.
	Grade 4 : Permanently discontinue MPDL3280A. Hold rociletinib until rash is Grade 1 and restart at one dose level lower (dose delays longer than 14 days require discussion with the Medical Monitor). If Grade \geq 3 rash recurs, rociletinib should
	be discontinued.
Diarrhea:	Grade 2 : Supportive care unless > 48 to 72 hrs. Then reduce dose of rociletinib and hold MPDL3280A until resolves to < Grade 1.
	Grade 3 : Hold rociletinib and MPDL3280A Obtain gastroenterology consult, discontinue NSAIDs or medications known to exacerbate colitis, Initiate steroid treatment. If resolves to < Grade 1, then restart rociletinib at next lower dose. If no recurrent symptoms, within 14 days resume MPDL3280A as long as steroid dose is ≤ 10 mg oral prednisone equivalent per day (dose delays longer than 14 days require discussion with the Medical Monitor).
	Grade 4 : MPDL3280A should be permanently discontinued. Hold rociletinib until diarrhea is Grade 1 and restart at one dose level lower. If Grade \geq 3 diarrhea recurs, rociletinib should be permanently discontinued (dose delays longer than 14 days require discussion with the Medical Monitor).
Nausea/Vomiting:	Grade1-2: Continue treatment. Begin maximum supportive care and adequate anti-emetic treatments (see Section 7.6.1 for guidance on avoiding QT-prolonging concomitant medication).
	Grade ≥ 3:
	 Begin/continue maximum supportive care and adequate combination anti-emetic treatments (see Section 7.6.1 for guidance on avoiding QT-prolonging concomitant medication). Consider gastroenterology consult;
	 Hold both rociletinib and MPDL3280A until < Grade 1. Restart rociletinib at next lower dose. If no recurrent symptoms, restart MPDL3280A;
	• If Grade \geq 3 nausea/vomiting recurs, MPDL3280A should be discontinued.

Toxicity	Attribution to both agents
Ocular Toxicity:	Grade ≥ 2:
	 Hold both study drugs until < Grade 1 (dose delays longer than 14 days require discussion with the Medical Monitor);
	 Obtain ophthalmology consult; uveitis or episcleritis may be treated with topical corticosteroid eye drops;
	 Reintroduce rociletinib at a reduced dose when symptoms resolved to Grade ≤ 1. If no recurrent symptoms, restart MPDL3280A; MPDL3280A should be permanently discontinued for immune-mediated ocular disease that is unresponsive to local immunosuppressive therapy.
Laboratory abnormalities	Grade \geq 3 Laboratory abnormalities related to study drug that are asymptomatic and deemed by the Investigator not to be clinically significant
	 After discussion between Investigator and Medical Monitor, rociletinib dosing may be delayed, and treatment subsequently resumed at the current dose level or at a reduced dose. If abnormality persists > 7 days, MPDL3280A dosing may also be held and subsequently resumed at the same dose level when toxicity resolves to baseline grade plus one.
Liver toxicities	Grade \geq 3 AST, ALT, or bilirubin abnormalities (or AST or ALT \geq 10 × ULN in patients with hepatic metastases) related to study drug that are asymptomatic and deemed by the Investigator not to be clinically significant
	• Hold both study drugs until recovery Grade ≤ 1 ;
	 Initiate systemic steroids IV for 48 hours followed by oral taper;
	 Monitor LFTs QOD until decreasing, then weekly;
	 If resolved to baseline grade plus one (eg, if baseline Grade 1, then Grade 2) resume MPDL3280A dosing;
	 If AE persists permanently discontinue MPDL3280A.
Other Grade ≥ 3 non-hematologic or Grade 4	 Hold rociletinib and MPDL3280A until recovery to Grade ≤ 1 and then restart rociletinib at a reduced dose and MPDL3280A at the same dose.
hematologic toxicity	 If the Grade 4 AE recurs (a second time), then MPDL3280A should be discontinued.
	 If the Grade 4 AE recurs (a third time), then rociletinib should be discontinued.

Table 18:Management of Overlapping Toxicities (continued)

Clovis Oncology, Inc. Rociletinib (CO-1686) FINAL Version 1.0

Table 18:	Management of Overlapping Toxicities (continued)	
-----------	--	--

Pulmonary toxicity	Incidental radiographic findings of ground glass opacities (GGO) or non-infectious infiltrate in absence of symptoms:
	 Hold rociletinib and MPDL3280A and re-evaluate after 1 week;
	 If no worsening in GGO/infiltrates and patient is still asymptomatic, resume treatment with rociletinib. Re-evaluate after additional 1 week. If GGO/infiltrates are still present and not worsened, perform pulmonary function tests. If patient is confirmed asymptomaic, resume treatment with MPDL3280A.
	 If GGO/infiltrates worsen and patient is still asymptomatic, continue to hold rociletinib and MPDL3280A and refer patient for bronchoscopy and pulmonary function tests. Consider starting low-dose oral prednisone 10 mg or equivalent per day. Re-evaluate after 1 week and resume rociletinib if GGO/infiltrates improve. Re-evaluate after additional 1 week and resume treatment with MPDL3280A under the same conditions.
	 Prior to reintroduction of rociletinib, discuss appropriate dose with Medical Monitor.
	Symptomatic presentation (eg, hypoxia, cough;Grade 2+):
	 Hold rociletinib and MPDL3280A dosing and investigate for presence of radiographic changes.
	 Rule out alternative causes (eg, lymphangitic carcinomatosis, infection, heart failure, chronic obstructive pulmonary disease, pulmonary embolism, or hypertension). Diagnostic evaluation may include oxygen saturation (ie, arterial blood gas), high-resolution CT scan of the chest, bronchoscopy with bronchoalveolar lavage, pulmonary function tests (with DL_{CO}), and pulmonary function testing with a pulmonary embolism protocol.
	 Grade ≥ 3 dyspnea or hypoxia may require corticosteroid treatment. MPDL3280A should be interrupted if corticosteroids are initiated.
	 Delay rociletinib and MPDL3280A re-administration if GGOs are observed. Administer steroids if pneumonitis or organizing pneumonia is documented.
	• If bronchoscopy is consistent with immune-related etiology, start oral prednisone 60 mg or equivalent per day, followed by a taper over 2 weeks.
	 Rociletinib dosing may be restarted at a reduced dose after resolution of symptoms and steroid use is no more than 10 mg prednisone equivalent per day. If no recurrent symptoms develop within 14 days, MPDL3280A dosing may be reinitiated.
	 Discussion between the Investigator and Medical Monitor and approval to restart dosing is required before rociletinib or MPDL3280A are restarted.
	 Permanently discontinue MPDL3280A for life-threatening immune-related pulmonary events.

Clovis Oncology, Inc. Rociletinib (CO-1686) FINAL Version 1.0

Toxicity	Attribution to both agents	
Amylase/Lipase	Grade ≥ 3 amylase/lipase elevation	
	 Delay MPDL3280A and rociletinib for asymptomatic Grade ≥ 3 amylase and/or lipase elevations and monitor QOD until decreasing; for Grade 4 elevations consider 10 mg prednisone daily; 	
	 If symptomatic, MPDL3280A and rociletinib should be held. Methylprednisolone or oral steroids (prednisone equivalent of 60 mg/day) should be administered. Rociletinib dosing may be restarted when symptoms resolve and the amylase/lipase elevation is Grade ≤ 1. If no recurrent symptoms after 14 days then MPDL3280A dosing may be reinitiated at the same dose level. 	
	 If the Grade ≥ 3 amylase/lipase elevation recurs with symptoms before MPDL3280A re-initiation then rociletinib should be permanently discontinued. 	
	 If the Grade ≥ 3 amylase/lipase elevation recurs with symptoms after MPDL3280A re-initiation then rociletinib should be held until amylase/lipase elevation is Grade ≤ 1 and the MPDL3280A permanently discontinued. 	
	 MPDL3280A should be permanently discontinued for life-threatening, immune-related pancreatitis. 	
Hypothyroidism	 No change in MPDL3280A dosing will be implemented for asymptomatic TSH elevation; start thyroid replacement hormone and monitor TSH weekly; 	
	 Delay MPDL3280A for symptomatic TSH elevation; start thyroid replacement hormone and monitor TSH weekly; resume MPDL3280A when symptoms improve and TSH is decreasing. 	

AE, adverse event; ALT, alanine aminotransferase; AST, aspartate aminotransferase; IV, intravenous; NSAID, nonsteroidal anti-inflammatory drug; QOD, every other day; TSH, thyroid-stimulating hormone; ULN, upper limit of normal.

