3.2.1 Dose-Limiting Toxicity

Determination of DLTs will be made during the first 21 days of combination treatment with rociletinib and MPDL3280A (ie, during Cycle 1 after the rociletinib Run-in-Period) in the Dose Finding Phase. A DLT is defined as a clinically significant AE or laboratory abnormality assessed as at least related to the study drug (rociletinib and/or MPDL3280A), unrelated to disease progression, and that meets any of the following criteria:

Cytopenia:

- Grade 4 neutropenia persisting for more than 7 days;
- Febrile neutropenia, defined as an absolute neutrophil count (ANC) < 1000/mm³ and a single temperature of > 38.3°C (101°F);
- Grade 4 thrombocytopenia persisting for more than 7 days or thrombocytopenia with clinically significant bleeding (ie, bleeding that requires blood or platelet transfusion or other medical intervention, or that may cause disability or death, such as cerebral hemorrhage).

Organ Toxicity:

• Grade \geq 3 symptomatic hepatic toxicities lasting for > 48 hours, or Grade \geq 3 asymptomatic hepatic toxicities lasting for > 7 days with the following exception:

- For patients with Grade 2 Alkaline phosphatase (ALP) abnormality at baseline, an increase to > 8 × the upper limit of normal (ULN) lasting > 48 hours (if symptomatic) or > 7 days (if asymptomatic) will be considered a DLT.
- Grade \geq 3 nonhematologic, nonhepatic organ toxicity, with the following exceptions:
 - **DLT Toxicity Exceptions**
 - Grade 3 nausea, vomiting, or diarrhea that resolves to Grade ≤ 1 within 7 days after starting appropriate supportive therapy (see Section 6.2.2);
 - Grade ≥ 3 asymptomatic or mildly symptomatic rash that can be adequately managed with supportive care (see Section 6.2.4) or symptomatic rash that resolves to become asymptomatic and/or Grade ≤ 2 within 7 days of appropriate supportive therapy;
 - Grade \geq 3 fatigue that resolves to Grade \leq 2 within 7 days;
 - Grade 3 arthralgia that can be adequately managed with supportive care or that resolves to Grade ≤ 2 within 7 days;
 - Grade 3 autoimmune thyroiditis or other endocrine abnormality that can be managed by endocrine therapy and that would not necessitate initiation of systemic corticosteroids;
 - Grade 3 fever (in the absence of any clinically significant source of fever) that resolves to Grade ≤ 2 within 7 days with supportive care;
 - Grade 3 laboratory abnormality that is asymptomatic and deemed by the Investigator to be not clinically significant;

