5.7 Dose Modification Guidelines

5.7.1 Study Treatment Dose Reductions

5.7.1.1 Rociletinib Dose Reductions

From a starting dose of 500 mg BID rociletinib, up to two dose reductions are available (Table 7). No dose reduction below 250 mg is permitted. All dose reductions are permanent.

Current Dosage	Dose Reduction
500 mg PO BID	375 mg PO BID
375 mg PO BID	250 mg PO BID
250 mg PO BID	No further dose reduction allowed

Table 7:Dose Reductions for Rociletinib

BID, twice daily; PO, oral.

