5.7.2 Phase 1 – Run-in-Period

Rociletinib monotherapy will be administered orally BID during the 7-day Run-in-Period. Dose reductions of rociletinib during the Run-in-Period are not allowed for reasons other than a DLT. Dose delays of rociletinib for up to 48 hours for toxicity management is allowed. Any patient who experiences an AE(s) that requires either a delay of treatment for more than a total of 48 hours or a dose reduction during the 7-day Run-in Period of rociletinib monotherapy will not be eligible for combination therapy. Such a patient will only receive monotherapy rociletinib for the duration of participation in the study.

5.7.3 Phase 1 – Cycle 1

The first dose of MPDL3280A at 1200 mg will be administered by IV on C1D1. Dose reductions of rociletinib are not allowed for reasons other than a DLT or a decision by the CSC based on emerging safety data. Dose delays of rociletinib are not allowed for reasons other than toxicity. Patients are eligible for safety and DLT evaluation of the cohort if they receive at least 75% of the planned total dose of each study drug within Cycle 1 or they experience a DLT at any time during Cycle 1.

5.7.4 Beyond DLT Assessment (Phase 1 – Cycle 2+ and Phase 2 – All Cycles)

For patients who experience a toxicity that is equivalent to a DLT – If the toxicity is assessed as being related to rociletinib, the next dose of rociletinib should be held until resolution of the toxicity to Grade 1 or to the baseline level (if severity > Grade 1 at baseline) and then reduced to the next dose level of rociletinib (Table 7), unless permanent discontinuation of rociletinib is required per toxicity management guidelines of the protocol (Sections 6.1 and 6.3). If the toxicity is assessed as being related to MPDL3280A, the next dose of MPDL3280A should be held until the toxicity has resolved to Grade 1 or to the baseline level (if severity > Grade 1 at baseline), unless permanent discontinuation of MPDL3280A is required per toxicity management guidelines of the protocol (Sections 6.2 and 6.3). In addition, because there is no available antidote for MPDL3280A and discontinuation of MPDL3280A may not have immediate therapeutic effect, consideration may be given to holding rociletinib doses temporarily even if the toxicity is not attributed to rociletinib.

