6 MONITORING AND MANAGEMENT OF EXPECTED OR POTENTIAL TREATMENT-RELATED TOXICITY

In general, toxicities should be managed with supportive care and with dose modifications for each of the study drugs (Section 5.7) according to attribution of the toxicity. Certain toxicities may be more likely to occur with rociletinib or MPDL3280A, and some toxicities may be overlapping. This section provides guidance on the monitoring and management of expected or potential toxicities associated with rociletinib or MPDL3280A or both rociletinib and MPDL3280A.

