11 PATIENT DISPOSITION

11.1 Permanent Discontinuation of Study Treatment

A patient must be discontinued from all study treatment if any of the following applies:

- Consent withdrawal at the patient's own request or at the request of their legally authorized representative;
- Clinical disease progression where the Investigator believes that the patient will not continue to benefit from study treatment (*Note:* patients will be permitted to continue study treatment after a radiographic progression [Appendix A: and Appendix B] if the benefit-risk ratio is judged to be favorable and continued treatment is approved by the Medical Monitor);
- Any event, adverse or otherwise, that, in the opinion of the Investigator, would pose an unacceptable safety risk to the patient;
- Any requirement for dose holds of rociletinib for more than 14 days or dose holds of MPDL3280A for more than 42 days, unless permission from the Sponsor's Medical Monitor for longer dose delay is granted;
- An intercurrent illness that, in the opinion of the Investigator, would affect assessments of the clinical status to a significant degree and requires discontinuation of therapy;
- A positive pregnancy test at any time during the study;
- Investigator decision.

In addition, the Sponsor may discontinue the study early for any of the reasons noted in Section 12.6.

The Sponsor (or designee) should be notified of all study terminations as soon as possible. The date and reason for cessation of PO rociletinib and/or IV MPDL3280A must be documented in the eCRF and source documents.

To the extent possible, EOT assessments should be performed for all patients who receive rociletinib and MPDL3280A. The EOT visit should occur 28 (\pm 7) days after the last dose of rociletinib and MPDL3280A. After stopping protocol-specified treatment, all patients will remain in the study and will be followed for safety (through 28 days after last dose; those with ongoing SAEs will be followed until either resolution or stabilization has been determined), for disease progression (every 8 \pm 1 weeks until disease progression), and for survival status and subsequent NSCLC therapies (at approximately quarterly intervals until death or Sponsor decision).

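### Table 18, rash row: a Grade 3 rash that recurs as Grade 4 meets two rules with different rociletinib restart doses, and no sentence says which governs

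*Combined protocol and SAP*

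**What the plan says.** Table 18 in Section 6.3 covers toxicities attributed to both drugs. In its rash row, a first Grade 3 rash stops both drugs temporarily. Once it has settled to Grade 1 or better, rociletinib resumes at a dose agreed with the Medical Monitor.

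The last bullet of the Grade 3 block deals with recurrence. It applies "if the patient experiences recurrent Grade ≥ 3 skin toxicity", ends MPDL3280A permanently, holds rociletinib, and continues: "When rash is Grade 1, restart rociletinib at previous dose".

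The Grade 4 line also ends MPDL3280A permanently. Its rociletinib instruction is: "Hold rociletinib until rash is Grade 1 and restart at one dose level lower". Nothing confines that line to a first episode.

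Three other places bear on the choice:

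- Section 6 says toxicities should in general be handled with supportive care and "with dose modifications for each of the study drugs (Section 5.7) according to attribution of the toxicity".
- Section 5.7.4 deals with a toxicity equivalent to a DLT and related to rociletinib. The next dose is held until recovery "and then reduced to the next dose level of rociletinib (Table 7"). The only exception it names is permanent discontinuation.
- Section 5.7.1.1 and Table 7 set the dose steps at 500, 375 and 250 mg BID, with nothing below 250 mg. They add: "All dose reductions are permanent".

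**The concern.** A recurrence trigger of Grade 3 or higher includes Grade 4, so the same event is covered by a rule that keeps the dose and by a rule that lowers it. A site that follows the bullet to the letter puts a patient whose rash worsened on rechallenge back on the dose being taken when the Grade 4 rash appeared. A patient with a first Grade 4 rash would get a lower dose. That ordering is hard to defend, and the protocol gives no reason for it.

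Two sites could also dose the same event differently. The choice lasts, because a reduction once made cannot be reversed.

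**Working it through.** The plan states no figure on this point, so the check sets the rules side by side and applies them to each dose in Table 7.

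**Step 1. The two rules for a Grade 3 rash that recurs as Grade 4**

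| Element | Grade 3 block, recurrence bullet | Grade 4 line |
|---|---|---|
| Trigger | Recurrent, Grade 3 or higher | Grade 4, first or later |
| MPDL3280A | Permanently stopped | Permanently stopped |
| Rociletinib hold | Until Grade 1 | Until Grade 1 |
| Rociletinib restart | Previous dose | One level lower |
| Next rash of Grade 3 or higher | Rociletinib stopped | Rociletinib stopped |

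Both triggers are met. The rules part only on the restart dose.

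**Step 2. Restart dose by dose at recurrence (Table 7)**

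Here the previous dose is taken to be the one in use when the rash recurred. Going back to a dose from before an earlier cut would contradict the permanence rule in Section 5.7.1.1.

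- At 500 mg BID: 500 against 375, ratio 500/375 = 1.33.
- At 375 mg BID: 375 against 250, ratio 375/250 = 1.50.
- At 250 mg BID: 250 against a reduction that Section 5.7.1.1 does not permit.

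The first case requires that the Medical Monitor agreed to no reduction after the first Grade 3 rash.

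**Step 3. Does any text settle precedence?**

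- The rash row is laid out by grade, which suggests that a Grade 4 event belongs to the Grade 4 line. But the row's wording crosses its own headings: the Grade 4 line also governs a later Grade 3 rash. The layout alone does not cancel the bullet's trigger.
- Section 6 points to Section 5.7 in general terms and ranks nothing.
- Section 5.7.4 gives the lower dose if the rash is DLT-equivalent and related to rociletinib. Not every Grade 4 rash is: for events of Grade 3 or higher, Section 3.2.1 excepts "symptomatic rash that resolves to become asymptomatic and/or Grade ≤ 2 within 7 days of appropriate supportive therapy".
- The rest of Table 18 leans the same way. Diarrhea (Grades 3 and 4), nausea/vomiting (Grade 3 or higher), ocular toxicity (Grade 2 or higher), symptomatic pulmonary toxicity and the row for other severe toxicity all restart rociletinib at a lower dose.

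The context favours the lower dose, but no sentence says that it prevails.

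**Step 4. How often?**

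The documents give no rash rate for the combination. For rociletinib alone, Section 1.3.1 reports rash in 6 of 148 patients (6/148 = 4%), all mild. For MPDL3280A, Section 6.2.4 says most rash was mild and self-limited. The sequence needs a Grade 3 rash attributed to both drugs, a rechallenge, and then a Grade 4 rash. These data suggest that it is very uncommon but do not give a frequency.

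**The case against.** The strongest reply is that the intended answer is clear. The Grade 4 line names the grade and has no first-event limit, Section 5.7.4 reduces the dose, and nearly every comparable row does too. Controls also exist. The Medical Monitor is involved from the first Grade 3 rash, a rociletinib hold beyond 14 days needs the Medical Monitor's permission, and the Clinical Safety Committee reviews safety data for all patients. Section 11.1 requires stopping all treatment for any event that in the Investigator's opinion "would pose an unacceptable safety risk to the patient". The table is also presented as guidance.

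Most of this stands, and it limits the size of the point. It does not remove the conflict. The bullet is explicit, and a site that follows it is reading it as written. Section 11.1 concerns stopping treatment and does not choose a restart dose.

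A reader might infer three stronger things, none of which the documents support:

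- That the patient goes back to full dose. The dose may already have been lowered by agreement after the first Grade 3 rash.
- That for a rash excepted from the DLT definition only the row's layout favours the lower dose. The other Table 18 rows favour it as well.
- That the trial's results are affected. Only one restart dose in an unusual sequence is at issue.

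**Conclusion.** The text is wrong as written, in a minor way that concerns patient safety. Two stated rules give different rociletinib doses for the same event, and neither is given precedence. The surrounding text makes the lower dose the better reading, so the error lies in the breadth of the bullet's trigger.

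The size is one dose step, with no executable reduction at 250 mg BID. This rests on reading the trigger literally and on taking the previous dose as the one in use at recurrence. The judgment that the sequence is very uncommon rests on single-agent data only. The ORR endpoint, the sample size and the planned analyses are unaffected.

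**What to change.** In Table 18, change the trigger of the Grade 3 recurrence bullet to *recurrent Grade 3 skin toxicity*, and add: *Any Grade 4 rash, first or recurrent, is managed under the Grade 4 line.*

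In the Grade 4 line, state what to do for a patient already on 250 mg BID. Without this, the edit would send such a patient to an instruction that cannot be carried out.

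Keeping the previous dose for recurrent Grade 3 rash can remain the sponsor's choice. The sponsor should note, however, that Section 5.7.4 would reduce the dose if that rash is DLT-equivalent and related to rociletinib, and should confirm which is meant.

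The cost is one changed trigger, one added sentence and one instruction for the lowest dose. No data, visits or patients are added, and the wording can go into the next amendment.
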